### **21.3.4 Replacement Devices**

If, during the course of the trial, the Tranquil device(s) assigned to a Study Participant are damaged or malfunction, the Study Participant will be asked to contact the Clinical Center staff to report the problem, arrange to return the set of devices to the Clinical Center, and receive a replacement pair from the Clinical Center. For behind-the-ear devices, the Clinical Center staff will contact the DCC who will send a replacement pair of devices from the stock on hand to the Clinical Center using overnight delivery. The Clinical Center staff will return the pair of devices (which includes the damaged or malfunctioning device(s)) to GHI directly. For in-the-ear devices, the Clinical Center will contact the DCC but send the malfunctioning devices directly to GHI, who will send a replacement pair.

### **21.3.5 Data Logging**

Each Tranquil device will be engineered with data-logging capabilities. Data that are captured include:

- Sound output of the device (encrypted to preserve blinding at the Clinical Center);
- Intensity of ambient sound;
- Total times used and average number of hours per use that the Study Participant has worn the device;
- Total number of times the Study Participant has removed and re-inserted the device;
- Length of intervals when participant has not used the device per interval and day; and
- Low battery indicator.

Data will be downloaded from the devices onto a laptop or tower computer supplied to each Clinical Center for that purpose. The downloaded data will be used to generate reports on the use of the SG devices to aid the Clinical Centers in monitoring protocol compliance. These and additional data will also be sent to the DCC. Instructions for downloading the data are described in Chapter 12, Protocol for Sound Therapy.

The DCC will send data related to the function of each device directly to GHI. This information will be encrypted and not available to the Clinical Centers. GHI will be responsible for reviewing the data within three days of receipt. If GHI determines that any device is not operating properly (i.e, a conventional device is not generating a sound signal or a placebo device continues to generate a sound signal for a longer period of time than expected), GHI will immediately notify the DCC, so that a properly working replacement device can be issued to the Study Participant.

---

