#### 12.2 Sound Generators

We will use a digital equivalent of the Tranquil model sound generator, manufactured by General Hearing Instruments, Inc. (GHI), as the SG for the TRTT. The new digital devices will be implemented with added features including data-logging capability to enable the Study Audiologist to monitor the Study Participant's use of and compliance with the SG. Additionally, each participant's sound-level exposure will be monitored and logged to determine whether the SGs or environmental sound is the primary sound exposure and the nature of the sound-exposure properties. The SG will be housed either in a behind-the-ear (BTE) instrument or in an all-in-

the-ear (ITE) non-occluding device, both of which will offer adjustment of the output volume to a “zero” (fully quiet) noise floor. GHI will provide both the standard and the placebo SG devices. The placebo SG will have specially designed sound properties, closely resembling key properties of the standard SG, and a physical appearance identical to the standard (conventional) instrument so that neither the Study Audiologist nor the Study Participant will be aware of which sound treatment the participant is receiving.

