### **12.3 Second Treatment Visit and Subsequent Care**

The second treatment visit (T2) occurs one month after T1 and is designed to ensure that the Study Participant is wearing and using the SGs as instructed. The Study Audiologist will discuss the following points at the T2 visit:

- Each SG's physical fit;
- Volume setting at mixing point;
- Compliance and use of the SGs by the participant (using downloadable data-logging history to check device use and compliance); and
- Any Study Participant problems or concerns associated with the SGs or their use.

If the Study Participant with hyperacusis has been comfortable with the volume setting of the SG for the previous month, then the volume setting will be increased to the mixing point (if tolerable). If not, then the volume setting of the SG will be incremented by programmable adjustment toward the “mixing point” level or continued at the original setting until the next scheduled follow-up visit, at which time the Study Audiologist will discuss with the Study Participant increasing the sound level of the device to a higher level.

The Study Audiologist will answer any questions that the Study Participant has about the use of the SG at this time, and again emphasize his or her availability, to address questions and concerns.

At each subsequent Follow-up Visit, the Study Audiologist will check on the condition of the SGs, the participant's schedule of use, and re-confirm appropriate “mixing points” for the participant. The data-logging memory for each SG should be downloaded to evaluate the compliance history and sound-level exposure history, and this information sent to the Data Coordinating Center for evaluation and storage. This data-logging information can be used to encourage and counsel the participant if his or her compliance is problematic. Typically, there would be no further instruction on use of the SGs, although the Study Participant will continue to be encouraged to use the devices for the minimum 8 hours each day.

---

References:

Gatehouse, S. (1999). Glasgow Hearing Aid Benefit Profile. Derivation and validation of a client-centered outcome measure for hearing aid services. *Journal of the American Academy of Audiology*, 10, 80-103.

---

---

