#### **17.2.4 Study Audiologist**

At least two Study Audiologists must be certified for each TRTT Clinical Center. One of these may serve as Clinical Center Director, Study Otolaryngologist, or as the Clinical Coordinator. The requirements for TRTT certification as Study Audiologists are to:

- Attend a TRTT training session concerning:
  - TRTT design and methods;
  - Study Participant recruitment;
  - Study Participant enrollment and randomization;
  - Study Participant education and informed consent;
  - Study Participant care and follow-up;
  - Clinical Center management;
  - Forms completion; and
  - ATH evaluation protocol.
- Read the TRTT Manual of Procedures;
- Review TRTT data collection forms;
- Have completed at least one year of clinical experience (post-clinical fellowship year) as an audiologist;
- Attend a TRT training session, comprised of training in directive counseling (DC) and use of sound therapy;

- Attend a training meeting on components comprising standard of care treatment (SC) from the SC Training/Protocol Monitor;
- Review the directive counseling DC technique videotape;
- Review the SC technique videotape;
- Review the sound generator (SG) fitting technique videotape;
- Submit one voice recording of a DC counseling session with a non-study (or dummy) patient;
- Submit one voice recording of an SC session with a non-study (or dummy) patient;
- Work with other TRTT personnel to complete two sets of Baseline Eligibility Visit and Randomization Visit data collection forms and materials for non-study patients;
- Complete an online TRTT Knowledge Assessment test; and
- Complete and submit a Personnel Request for Certification form.

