**Table 23.1 Schematic showing the three study groups**

	Sound therapy	“Counseling”
Group 1 (TRT)	Conventional Sound Generator	DC
Group 2 (partial TRT)	Placebo Sound Generator	DC
Group 3 (Standard of care)	Recommendation to use ambient sound	Standard clinical consultation as provided in the military

Randomization helps to ensure that treatment groups are balanced with respect to pretreatment characteristics, although analyses of departures from balance will be carried out with appropriate adjustment to treatment effect estimation, if needed. Randomization will be performed using permuted blocks of random size, and stratified by Clinical Center. The logistics of the randomization are described in Chapter 5, Patient Entry into the Study.

An important feature of this study is that every effort is made to keep the Study Audiologists and Study Participants blinded with respect to the type of sound generator (SG), either conventional or placebo.

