### **24.4.1 Study Documents**

Study documents such as forms and manuals of procedures will be released for the information of individuals outside the FIG at appropriate times during the course of the study. The STC will decide which documents are to be released and the timetable for their release. Documents that are released will be placed in the library of the National Technical Information Service in Springfield, Virginia. Individuals wishing to access released study documents may apply to the NTIS using whatever application procedures are in force at the time of application.

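### Section 21.3.5 of the Manual that Study Audiologists must read implies that a working placebo device falls silent, an avoidable risk to the device blind in the secondary Group 1 versus Group 2 comparison

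*Combined protocol and SAP*

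**What the plan says.** Section 12.2 describes a placebo sound generator that looks identical to the conventional one and closely resembles it in key sound properties, so that "neither the Study Audiologist nor the Study Participant will be aware of which sound treatment the participant is receiving". Section 23.1.1 repeats this aim for audiologists and participants.

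Section 21.3.5 (Data Logging) protects the blind in two ways. Logged sound output is encrypted from the Clinical Centers, and so are the device-function data that the DCC passes to the manufacturer. The same section then gives the manufacturer examples of a device that is not working properly. One is that "a conventional device is not generating a sound signal". The other is that "a placebo device continues to generate a sound signal for a longer period of time than expected".

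Chapter 21 is part of the Manual of Procedures (Section 16.6 uses that name for the whole document). Certification as a Study Audiologist includes the requirement to "Read the TRTT Manual of Procedures" (17.2.4). Each Clinical Center must hold the Manual (17.3) and each Clinical Coordinator is given a copy (18.4.2.3); a Coordinator may also serve as a Study Audiologist (18.4.2.1). Section 24.4.1 adds that "manuals of procedures will be released for the information of individuals outside the FIG at appropriate times during the course of the study". The part of the document available for review contains no restriction on who may read Chapter 21.

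**The concern.** The plan treats the output behaviour of the devices as unblinding information, since it encrypts that information. It then prints, in text that the blinded staff must read, a criterion from which the difference in behaviour can be inferred.

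The treating audiologist has occasions to meet the cue. At each follow-up visit "the Study Audiologist will check on the condition of the SGs" and re-confirms the mixing points (12.3). The audiologist also asks about volume and about forgetting the instruments (Chapter 11, Appendix D), and records the acoustic output of replacement devices (14.8.3). A participant's remark that the sound has gone tells an uninformed audiologist little. It tells more to one who has drawn the inference from 21.3.5.

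At stake is Group 1 versus Group 2, the plan's test of sound therapy (23.1.3). Both groups receive directive counseling, with follow-up contacts at one month and at 3, 6, 12 and 18 months. The outcome is the self-reported Tinnitus Questionnaire (TQ). If audiologists came to know or suspect device type and encouraged the two groups differently, the result would be mixed with the device effect, and no later analysis could separate them.

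**Working it through.** **Step 1: what the fault criteria imply.** The plan states no figure on this point, so the main check is a comparison of texts.

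| Device | Fault according to 21.3.5 | Implied normal behaviour |
|---|---|---|
| Conventional | gives no sound | sound continues |
| Placebo | sound lasts longer than expected | sound lasts a limited time |

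The second row is an inference from a definition of malfunction, not a direct description. The expected duration is not given.

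**Step 2: who is meant to be blind, and who reads the text.** Sections 12.2 and 23.1.1 say Study Audiologists are to be blind to device type. Section 17.2.4 requires the same people to read the Manual. Nothing in the reviewed part exempts them from Chapter 21 or provides a separate site edition. Only Part 2 of 2 was available, so Part 1 could contain a restriction or a further disclosure.

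**Step 3: who needs the criteria.** Under 21.3.5 the manufacturer reviews the function data and notifies the DCC of a fault. The sites never apply the criteria.

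**Step 4: sensitivity of Group 1 versus Group 2 to a spurious shift.** Inputs from 23.2.3: SD 12.5, 76 per arm, 10% attrition, 80% power for 7 points, and an alpha of 0.05 divided among three comparisons, taken here as equal shares of 0.05/3 = 0.0167.

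These inputs agree with the plan's own sample size. A two-sided two-sample calculation for 7 points gives 67 per arm. Then 67/0.9 = 74.4, rounded up to 75, and 3 × 75 = 225, against the stated 228.

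For the illustration:

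- Analysed per arm: 76 × 0.9 = 68.4, taken as 68.
- SE of the difference: 12.5 × √(2/68) = 2.144 points.
- Two-sided t test with 134 degrees of freedom: critical value 2.424, so a difference beyond 2.424 × 2.144 = 5.20 points is declared significant.
- With no true device effect and a spurious mean shift b, the noncentrality is b/2.144.

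| Spurious shift b (TQ points) | b/SE | Probability of declaring a difference |
|---|---|---|
| 0 | 0 | 1.7% |
| 1 | 0.47 | 2.9% |
| 2 | 0.93 | 7.1% |
| 3 | 1.40 | 15.7% |

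The shifts are assumptions with no source in the documents. The table shows only how the test would respond if a shift occurred. It uses a single time point, whereas the plan's main analysis is longitudinal.

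**The case against.** The case on the other side is substantial, and most of it limits the point rather than removing it.

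- **A reader might infer that audiologists can sort the devices.** The documents do not support this. Section 12.2.5.3 prepares participants for the sound becoming undetectable, in some people almost at once, so conventional users may also report hearing nothing. The site's data-log summary shows hours in each memory and time not worn, not output (Chapter 12, Appendix A). Nothing says whether the placebo sound restarts when the device is reconnected, so re-confirming a mixing point may reveal nothing.
- **A reader might infer that counseling is free to drift.** It is not. Chapter 11, Appendix D is a script, training tapes cover follow-up sessions (20.6), and treatment sessions are recorded and sampled for adherence, with retraining for failures (16.5.2). However, the length and topics of follow-up sessions vary with the participant, so some room for differential encouragement remains.
- **A reader might infer that the Manual will be published mid-trial.** Section 24.4.1 leaves the choice of documents and the timing to the Steering Committee, and Section 24.4 warns against inappropriate unblinding through access to study information. These are general safeguards; neither mentions this text.
- **A reader might infer that the whole trial's blinding fails.** A second audiologist at each center stays blind to assignment (17.2.1), and Group 1 versus Group 3 does not rest on device blinding because Group 3 receives no device.

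What stands is the conflict itself. The masking effect of the advice to participants is weaker once staff know that silence may be a property of the placebo.

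**Conclusion.** The point holds as an avoidable risk of unblinding. The fault criteria in 21.3.5 allow the inference that placebo sound is time-limited, and the people meant to be blind must read them. That conflicts with 12.2, with 23.1.1 and with the encryption in 21.3.5 itself. The safeguards listed above reduce the risk without removing it.

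The documents do not show that anyone was unblinded, that the devices can be told apart in practice, or that any bias arose. The exposed comparison is Group 1 versus Group 2, a secondary objective. The primary comparison and the sample size are unaffected. If a bias of 1 to 3 TQ points did arise, the false-positive rate would be 2.9% to 15.7% instead of 1.7%, under the assumptions in the working.

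This is something that should be fixed, not a defect that invalidates the design. The conclusion also assumes that Part 1 neither restricts access to Chapter 21 nor discloses the placebo's behaviour openly.

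**What to change.** 1. In the site edition of 21.3.5, replace the parenthesis with neutral wording such as *is not operating to specification*.
2. Hold the type-specific fault criteria in a document restricted to the DCC and the manufacturer.
3. Check the rest of the Manual, including Part 1, for similar text before reissue.
4. State that no document describing how the placebo sound behaves is released to sites or to the public until follow-up ends.

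The cost is one reworded parenthesis, a reissued chapter and a separate restricted document to maintain. Devices, data collection and sample size do not change. The edit protects staff certified later and guards against outside release. It cannot undo what certified staff have already read, and Section 21.3.3 indicates that this edition dates from after the trial had begun.

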### **22.1 Introduction**

The Data Coordinating Center (DCC) is responsible for providing for study design, study information management design, data analysis, and interpretation. The goal and responsibility of the DCC is to work with the Clinical Centers to ensure that appropriate, complete and high quality data are assembled and that a study data base is developed and maintained throughout the course of the study that allows for appropriate and correct analyses of the interim and final data. Study information management includes database design and administration, forms development and data acquisition, data and forms tracking, quality assurance, and data security. The TRTT database will be web-based and managed at the Center for Clinical Trials at the Johns Hopkins Bloomberg School of Public Health.

### **22.2 Database Design, Development and Administration**

The major functional features of the proposed data management system include mechanisms for data acquisition, management, and transfer; a monitoring system to track participant visits and data collection forms, and completion of study milestones (e.g., accrual of participants, inventory of data completed); quality assurance procedures to insure validity and integrity of data

entered into the central research information system; and security features to insure the integrity of data. Detailed descriptions of each feature are explained below.

### **22.2.1 Design and Development**

Study database design consists of defining each of the data sources and the relationship between data sources and then constructing a database structure that efficiently stores and maintains the data inter-relationships of data elements. This generally begins with defining at least one data table per data source and defining key variables that will be used to preserve the ability to uniquely access each data record and link each to other records as study needs dictate. The standardized indices in the TRTT data management system will include the site ID, participant ID and alphabetical ID code ( name code), and date of visit. This infrastructure provides for data management, efficient tracking of Study Participant status, and development of performance monitoring and other quality assurance reports.

To facilitate design of data collection tools, a comprehensive data dictionary will be constructed to capture information about each data item. The item designator, item name, description, valid ranges or contents, width, format (i.e., date, numeric, text), item skip patterns based on data responses, and cross-item logical checks will be entered into the data dictionary, using manually defined definitions. The data dictionary will be maintained in both hard copy and electronic database formats at the DCC.

### **22.2.2 Database Administration**

Database administration includes the management of hardware and software components that comprise the system, implementation of back-up and recovery of data, and assignment of account privileges to control the functions each user is permitted to perform. These services will be regularly performed by the Director of Information Management.

### **22.2.3 Participant Status Tracking**

The database tracking system will monitor and record the Study Participant status as he or she moves from initial screening through randomization, enrollment, and follow-up study visit completion. Whenever there is a status change, the date and result, (e.g. eligible, yes or no) will be recorded, along with room for a comment. These procedures provide an historical record to track each recruit's status, and are especially important in tracking the status of those individuals whose eligibility is pending (see Chapter 5, section 5.3.2).

On-demand reports of the status of Study Participants using the participant status tracking module will enable study staff to monitor recruitment progress closely and compare it against

TRTT recruitment goals. If recruitment is lagging, the DCC staff can readily see at what stage the problem exists. With this information, the Steering Committee (STC) can then make informed decisions about modifications to the design, such as relaxation of certain eligibility criteria. This early warning system will maximize the opportunity to correct recruitment problems in the initial phase of the study.

#### **22.2.4 Randomization**

During the study database design, tables of randomized treatment assignments will be created. These tamper-proof tables will contain already generated random assignments that will be allocated at the time of randomization. These tables will contain randomly permuted blocked allocations, stratified by Clinical Center, and will be accessible online or by DCC staff if and when a Clinical Center telephones for a randomized treatment assignment.

A standard report will be generated at randomization, which will be available online immediately following randomization. It will designate the kit ID assigned to the Study Participant. The actual assignment, TRT (Directive Counseling (DC) and sound generator (SG)), or the standard of care (SC), will be contained within the kit itself. If assigned to TRT, the kit will also include the pair of Sound Generators to be used for Study Participants assigned to TRT.

#### **221.2.5 Scheduling Study Visits**

The database will be designed to assess the date of the Initial Treatment Visit (T1) to determine the dates and acceptable windows for Follow-up Visits for each Study Participant. A personalized study schedule will be generated for each Study Participant. Separate schedules will be generated for the treatment visits occurring at one month following T1, and for follow-up visits taking place at 3, 6, 12, and 18 months after T1. These schedules will serve to inform Clinical Center staff of the appropriate dates to schedule upcoming visits as specified in the protocol. In addition to the appointment schedules, email reminders will be generated at least one month before a study visit is due and sent to the Clinical Center staff scheduling the study visits. These reports will also be available on the TRTT website.

